8.3.2 Reporting of Pregnancy

Any finding of a positive pregnancy test or notification of the same should be reported to the VaxInnate Study Physician within 72 hours of notification:

[name]
Email: [contact] or his designee
[name] Email: [contact]

VaxInnate Corporation
[name]
[name]
[contact] cellular [contact] or [contact]
[name] [contact]

Pregnancy is not considered an adverse event, but is reportable to the IRB and CBER in the annual report. Administration of further doses of vaccine should cease immediately, although the subject should be followed for the usual safety

evaluations and blood draws. The pregnancy progress, state of prenatal care, and safety and outcome of mother and child (if the pregnancy is taken to delivery) should be followed and reported to the Sponsor.

8.3.3 Procedures to be Followed in the Event of Abnormal Laboratory Test Values or Abnormal Clinical Findings

A grading scale for abnormalities of clinical laboratory measures mandated by the protocol is provided as **Appendix B**. Isolated clinical laboratory abnormalities may be adverse events in themselves, and should be reported as adverse events if they raise clinical concern or are sufficient to initiate additional diagnostic tests. Clinical laboratory abnormalities that form part of a coherent clinical syndrome (e.g., transaminase elevations in well-defined hepatitis as described in **8.1.3** above) need not be listed as separate adverse events so long as the syndrome of which they are components is captured (e.g., it is not necessary to capture “hepatitis” and “elevated hepatic transaminases” and “anorexia” separately – the first of these includes the latter two). Clinical laboratory abnormalities that are reported as adverse events should be followed to resolution, and ancillary case report forms will be provided to capture these data.

8.3.4 Type and Duration of Follow-up of Subjects after Adverse Events

All AEs should be followed to resolution. AEs persisting to the final follow-up should be followed until the symptoms resolve or stabilize. Then the subject will be referred to their local physician.

8.4 Halting Rules

- If one or more subjects experience a clinically significant AE or laboratory abnormality (Grade 3 or 4), there will be no further enrollment until a full safety review is performed.
- The study will be halted (no new enrollments and no further investigational product administered) if one of the following occurs:
 - c. One subject experiences a serious adverse event (SAE) assessed as possible, probably or definitely related to investigational product or
 - d. There is a subject death assessed as possibly, probably or definitely related to investigational product.

8.5 Safety Oversight

VaxInnate will serve as the Sponsor for this study. Sponsor responsibilities will include the creation and oversight of the protocol development, submission of the Investigational New Drug (IND) application to the Food and Drug Administration (FDA), monitoring and ensuring Good Clinical Practice (GCP) conduct of the study, and the submission of annual and final study reports to the FDA.

If there appears to be a safety issue which would cause the halting of the trial, the site will alert VaxInnate and inform them of their findings.

A safety monitoring committee (SMC) comprised of a Principal Investigator from each site, VaxInnate, and an Independent Safety Monitor, will be set-up to assess in a blinded fashion the safety and reactogenicity should one of the above halting rules be met. The Independent Safety Monitor may be unblinded to study treatment, as needed, to adequately assess safety issues.

If the trial is halted or amendments are recommended, the sites' IRBs, and FDA will be notified.

9 DATA COLLECTION, PROCESSING AND ANALYSIS

9.1 Data collection and processing

Subject screening/enrollment will be documented using an electronic master subject log. This log will capture the following information: subject number, initials, date screen/enroll and reason for not enrolling.

In this study, CRFs utilizing Smart Pen™, a digital pen technology, will be used to gather originally-captured data. Therefore, the CRFs will serve as the source document for all protocol procedures and assessments, except for concomitant medications, adverse events, and all "Symptom Assessments" obtained from subject-completed memory aids (MEMA CRF). For these required procedures and assessments, the collected data will be recorded onto logs or memory aids as source documentation. This data will then be transcribed onto the CRF by the study staff. An electronic data management system will be used to create, modify, maintain, archive, retrieve, and transmit study data.

The Investigator remains responsible for the accuracy and adequacy of all data entered on the CRFs. Data will be monitored as described in **Sections 10.7 and 10.8**. Under direction of the clinical monitor, CRFs will be source data verified, as appropriate and further processed. Upon further data processing, queries may be generated and sent to the Investigator for clarification or correction. The Investigator will address any queries and resolutions verified by the clinical monitor.

9.2 Statistical methods

9.2.1 Overview and Study Objectives

A multicenter, double-blind, randomized, placebo controlled vaccine study to assess the safety, reactogenicity and immunogenicity of two groups receiving TIV with 1 µg VAX102 investigational vaccine, delivered intramuscularly as a prime vaccination, compared to TIV with placebo, in healthy normal adults of both genders.

The objectives of the study are:

Primary: To assess the safety, reactogenicity, and tolerability of VAX102 when given with Trivalent Inactivated Influenza Vaccine (TIV) delivered in the same arm as two separate IM injections in healthy adults 18 to 49 years.

Secondary:

- To assess the immunogenicity of the VAX102 vaccine when given with TIV.
- To assess the antibody response to TIV when given with VAX102 compared to TIV alone.

9.2.2 Sample size and power

Selection of sample size is arbitrary, and chosen to be appropriate to the phase II nature of the trial.

9.2.3 Analysis populations

- The safety population will consist of all subjects who received at least one immunization of investigational product (vaccine).
- The primary immunogenicity population will consist of all subjects who receive both immunizations of study treatment (VAX102 or placebo and TIV) and have baseline and Days 14 and 28 (± 2) anti-M2e or HAI serum antibody titers, and who have no major protocol violations that could compromise the interpretation of immunology results.

9.2.4 Study Hypothesis

The hypothesis is that the VAX102 vaccine with TIV, administered IM, will be generally well-tolerated and will elicit M2e or HAI antibodies respectively in at least one dose level tested, that are comparable to, or greater than, those elicited by the placebo (F105) with TIV delivered IM.

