
HALTING RULES
	
 1. If one or more subjects experience a clinically significant AE or laboratory abnormality (Grade 3 or 4), there will be no further enrollment until a full safety review is performed. 2. The study will be halted (no new enrollments and no further investigational product administered) if one of the following occurs: 
 a. One subject experiences a serious adverse event (SAE) assessed as possible, probably or definitely related to investigational product or b. There is a subject death assessed as possibly, probably or definitely related to investigational product. 
A safety monitoring committee (SMC) comprised of a Principal Investigator from each site, VaxInnate, and an Independent Safety Monitor, will be set-up to assess in a blinded fashion the safety and reactogenicity should one of the above halting rules be met. The Independent Safety Monitor may be unblinded to study treatment, as needed, to adequately assess safety issues.

FOLLOW-UP DURATION	Volunteers will be followed for 28 days after the Day 0 vaccination.
ENDPOINT PARAMETERS	
a) Safety analysis includes:
 
 • Standard descriptive demography and reactogenicity from the memory aid will be assessed. All subjects who receive any investigational product will be included in the safety analyses. • Subjects with adverse events (including clinical laboratory abnormalities) will be summarized by MedDRA body organ system and preferred term, severity, relatedness and, separately, by seriousness. 
b) Immunogenicity parameters include:
 
 • Geometric mean of pre- and post-vaccination anti-M2e or HAI serum antibody concentrations. • Change from pre- to post-vaccination geometric mean of anti-M2e or HAI serum antibody concentrations. • Proportion of subjects with an M2e and HAI-specific serum antibody titer before vaccination. • Proportion of subjects with an M2e and HAI-specific serum antibody titer after vaccination. • Descriptive analysis of HAI titers in subjects who received TIV plus VAX102 compared to TIV plus Placebo.

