8	SC	0.3	0.7	0.4	1.8
8	SC	1	0.8	0.6	2.1
8	SC	2	1.9	0.8	3.2
8	ID	0.3	0.4	0.4	1.3
8	ID	1	1.8	0.7	2

Summary of Preclinical data supporting HAI enhancement with mice

[figure not shown]
In 2007 Flulaval was tested in combination with STF2 or VAX102 in three different experiments. The H1 HAI was measured against New Caledonia (**Table 5**). In all three experiments the combination of TIV with VAX102 demonstrated a three to five fold increase in HAI titer compared to Flulaval alone.

Study & report date	1	2	3
	Sept '07	Oct '07	Dec '07
Flulaval	130	61	95
Flulaval + STF2	299	127	-
Flulaval + VAX102	686	175	428
Flulaval + VAX102 + alum	-	-	538
Flulaval to Flulaval + VAX102 fold increase	5.3	2.9	4.5

Note: 15-20 mice in each group

A similar enhancement was demonstrated for the Sanofi H5 pandemic vaccine. In this experiment (Figure 2), the combination of Sanofi H5 given with VAX102 given in the same limb showed a marked increase in HAI H5 (VN) titer.

Figure 2. Enhancement of H5 HAI response with concomitant administration of VAX102

Rationale for current study

VAX102 is immunogenic in healthy adults. An average 6-fold increase in the H1 HAI GMT is a good indication of efficacy for the H1 component of a recombinant trivalent vaccine (Table 5). We also know that the flagellin component is able to activate the immune system via the innate immune pathway. In animal studies we have shown that this immune activation can enhance the immune response to inactivated seasonal and pandemic influenza vaccines. The immunopotential of the HAI immune response could be important clinically in groups like the elderly who respond poorly to TIV. The purpose of this study is to test the safety and immunogenicity of this novel adjuvant-antigen in combination with trivalent inactivated influenza vaccine in young healthy adults 18-49 years of age to determine if this combination is safe and able to adjuvant the TIV immune response. If successful, the plan is to test the combination in the elderly in a subsequent study.

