9.2.5 General statistical analysis methods

In general, all data collected will be listed. Categorical variables will be summarized by dose group as frequencies and percentages in each category. Continuous variables will be summarized by dose group as numbers of subjects, means, standard deviations, medians, and minimum/maximum values. Two-sided, 95% confidence intervals will be calculated for immunogenicity endpoints and differences between each dose group.

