9.2.9 Immunogenicity analysis

Immunogenicity parameters will be listed for all subjects and summarized and analyzed for the primary and secondary immunogenicity populations separately.

M2e and HAI specific IgG antibody titration curves will be established at each time point that data are available. At the start of the study volunteers will be scored as positive (IgG titers above an established negative baseline) or negative (IgG titers below the negative baseline) for pre-existing M2e or HAI specific IgG titers. The proportion of sero-negative volunteers who develop significantly positive antibody titers after immunization in each Group will be determined. The proportion of sero-positive volunteers who develop a significant rise in antibody titers after immunization in each Group will also be estimated. Standard statistical analyses will be used to distinguish significant changes in antibody titers. One-sided 95% lower confidence bound on the estimated proportion will also be constructed. All analyses will be based upon a per-protocol cohort with additional analysis performed for the intent-to-treat (ITT) cohort. The per protocol cohort is defined as all volunteers who complete both immunizations (VAX102 or placebo plus TIV).

Anti-M2e or HAI serum antibody titers will be listed and summarized for each time point that data are available. The mean change from baseline to Day 28 (± 2) in the log-transformed anti-M2e or HAI serum antibody reciprocal titers will be compared to zero within dose groups using t-tests. Analysis of variance (ANOVA) will be used to test for differences among dose groups, with Dunnett's test used to compare each dose group. Dose-response will be tested using vaccine and the amount of antigen in μg per group, coded as 1 μg or placebo. Pairwise comparisons will be used to evaluate differences between Groups. Proportion of subjects with an immune response at Days 14 (± 2) and 28 (± 2) will be compared among Groups using a Fisher's exact test or chi square test of association.

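### The immunogenicity hypothesis accepts antibodies 'comparable' to placebo plus TIV without defining comparable, so a null or moderately lower HAI result could be read as support for it

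*Protocol*

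**What the plan says.** Protocol Section 9.2.4 says that VAX102 with TIV will be generally well tolerated and "will elicit M2e or HAI antibodies respectively in at least one dose level tested", and then sets the standard for those antibodies: "that are comparable to, or greater than, those elicited by the placebo (F105) with TIV delivered IM".

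Five other places bear on it:

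- **Purpose.** The rationale in Section 1 says the study is "to determine if this combination is safe and able to adjuvant the TIV immune response", and makes a later study in the elderly depend on success.
- **Between-group tests.** Section 9.2.9: "Analysis of variance (ANOVA) will be used to test for differences among dose groups, with Dunnett's test used to compare each dose group". Responder proportions "will be compared among Groups using a Fisher's exact test or chi square test of association".
- **Intervals.** Section 9.2.5: "Two-sided, 95% confidence intervals will be calculated for immunogenicity endpoints and differences between each dose group". No threshold is attached.
- **Size.** Section 9.2.2 calls the sample size arbitrary. Section 3 gives 40 per group, randomized 1:1, with one VAX102 dose level.
- **Synopsis.** The endpoint list has "Descriptive analysis of HAI titers in subjects who received TIV plus VAX102 compared to TIV plus Placebo", whereas Section 9.2.9 tests HAI formally.

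**The concern.** Whether VAX102 can adjuvant TIV is a superiority question. Section 9.2.4 replaces it with a standard that no increase would also meet, and does not say how close counts as comparable. Because the between-group methods look for a difference, the outcome most easily taken as comparable is a non-significant p-value, and in a trial of unplanned power that is weak evidence of similarity. A moderate loss of HAI response could then be written up as agreeing with the hypothesis.

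For M2e the difficulty is the comparator. Section 1 says that natural infection and current vaccines fail to induce significant M2e antibody, so Group B should have almost none. Being comparable to Group B on M2e would describe a vaccine that had not worked.

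Two further phrases add doubt. The dose-level clause assumes several doses where there is one. Joining M2e and HAI by 'or' and then adding 'respectively' leaves it open whether either antibody suffices or each must respond.

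**Working it through.** There is no power calculation to reproduce: Section 9.2.2 gives no alpha, power, SD, effect or margin.

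**HAI inputs.** From the Protocol: 40 per group, and two-sided 95% intervals (Section 9.2.5). Assumed: tests at two-sided 5%, all subjects evaluable, and an SD of log10 titer (or log10 change) of 0.5, 0.6 or 0.7, since the Protocol states none. With two groups the ANOVA is the two-sample t-test, with 78 degrees of freedom and critical value 1.991.

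**How low the observed ratio must be.** SE = SD × √(2/40) = SD × 0.2236. The result is significantly lower when the observed GMT ratio A/B is below 10^(−1.991 × SE).

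| SD | SE | 1.991 × SE | Ratio must be below |
|---|---|---|---|
| 0.5 | 0.1118 | 0.223 | 0.60 |
| 0.6 | 0.1342 | 0.267 | 0.54 |
| 0.7 | 0.1565 | 0.312 | 0.49 |

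**Probability of not being significantly lower.** Non-central t with 78 degrees of freedom and non-centrality |log10(true ratio)| / SE. For a ratio of 0.67, |log10| = 0.174. For 0.5, it is 0.301. At SD 0.5 the non-centralities are 0.174/0.1118 = 1.56 and 0.301/0.1118 = 2.69.

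| True GMT ratio | SD 0.5 | SD 0.6 | SD 0.7 |
|---|---|---|---|
| 0.80 | 86.5% | 89.4% | 91.1% |
| 0.67 | 66.4% | 75.2% | 80.6% |
| 0.50 | 24.2% | 39.9% | 52.4% |

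At a true ratio of 1 the figure is 97.5% whatever the SD. At a smaller SD of 0.4 the rows become 81.3%, 51.6% and 8.6%. All figures are for one strain.

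**M2e.** After one dose of 0.3 or 1.0 µg in VAX102-01, 18/24 = 75% responded (Section 1). If Group B has 0/40 responders, two-sided Fisher tests give:

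- 0/40 in Group A: p = 1.00
- 5/40: p = 0.055
- 6/40: p = 0.026

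So 5/40 = 12.5% responders in Group A would not differ significantly from placebo. If the true rates were 75% against 0% to 10%, power at 40 per group would be essentially 100%. A superiority hypothesis for M2e therefore needs no more subjects.

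**The case against.** The strongest reply is that the Protocol never says a non-significant ANOVA will be called comparable, and that Section 9.2.5 already plans two-sided 95% intervals for group differences. Immunogenicity is a secondary objective in an openly exploratory trial, and the objective on TIV is worded neutrally, so HAI non-interference is a fair question for two vaccines given together. A criterion could also be set in a statistical analysis plan not seen here. Most of this stands. It is why the fix uses the planned interval and leaves room for a non-interference claim. It does not cure a hypothesis that, as worded in the Protocol, a null result can support, and no margin would make similarity to placebo a sensible M2e aim.

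A reader might go further, in three ways the document does not support:

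- **That almost any result confirms the hypothesis.** A significantly lower HAI response or poor tolerability would count against it. A halved HAI response would be flagged in about 48% to 76% of trials at SD 0.5 to 0.7, per strain. With H1, H3 and B all measured, a loss in all three would be seen more often if any one strain counted. And where there is truly no difference, calling the groups comparable is correct, so the 97.5% is not by itself an error rate.
- **That a nil M2e response confirms it.** On the natural reading it fails, because antibody must be elicited, 'respectively' ties M2e to VAX102, and Section 9.2.9 tests the within-group change against zero. It would pass only if 'or' means either antibody, or if the comparison is read alone.
- **That the decision on an elderly study rests on Section 9.2.4.** Section 1 ties it to safety and to adjuvanting TIV, which a merely comparable result would not meet.

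**Conclusion.** The point holds as a fault in the stated hypothesis. Section 9.2.4 has no criterion for comparable, is accompanied by tests of difference, and does not match the adjuvant purpose in Section 1. A null or moderately lower HAI result could be read as supporting it: at a log10 SD of 0.5 to 0.7, a one-third loss would escape a significantly-lower finding in roughly two-thirds to four-fifths of trials, and a halving in roughly a quarter to a half. These sizes rest on the assumed SDs, full evaluability, one strain at a time, and a reader taking non-significance as comparability. For M2e the comparison is the wrong criterion under any SD. The 'M2e or HAI' wording is ambiguous and the dose-level clause does not fit a one-dose trial. The mismatch between the synopsis and Section 9.2.9 on HAI is minor.

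**What to change.** Rewrite Protocol Section 9.2.4:

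1. **M2e:** the response in Group A exceeds that in Group B.
2. **HAI:** for each of H1, H3 and B, the Group A GMT exceeds the Group B GMT at Day 28, judged by the GMT ratio A/B and the two-sided 95% confidence interval already planned in Section 9.2.5.
3. **Reading of a null result:** a non-significant HAI difference is not reported as comparability. If the sponsor wants a non-interference claim, it rests on the same interval against a margin stated and justified in advance.

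Delete the clause about at least one dose level, and replace the 'or ... respectively' construction with separate statements for the two antibodies. Align the descriptive HAI line in the synopsis with Section 9.2.9.

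This is a change of wording, with no added subjects, visits or assays. The sponsor gives up a hypothesis that a null result could support. It should also know what 40 per group can show on HAI. By the normal approximation, 80% power needs a true GMT ratio of 10^((1.960 + 0.842) × SE), which is 2.06, 2.38 or 2.74 at SD 0.5, 0.6 or 0.7. For non-interference with a true ratio of 1 and, purely as an illustration, a 2-fold margin, power is 77%, 61% or 49%. With a 1.5-fold margin it is 35%, 26% or 20%.

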9.2.5 General statistical analysis methods

In general, all data collected will be listed. Categorical variables will be summarized by dose group as frequencies and percentages in each category. Continuous variables will be summarized by dose group as numbers of subjects, means, standard deviations, medians, and minimum/maximum values. Two-sided, 95% confidence intervals will be calculated for immunogenicity endpoints and differences between each dose group.

9.2.6 Baseline characteristics

Baseline characteristics will be listed and summarized and will include inclusion/exclusion criteria; demographics (e.g., age, sex, race/ethnicity); medical history.

9.2.7 Study drug administration

Details of study vaccine administration will be listed. In addition, a summary tabulation will be produced that shows the number of subjects in each group who received 1 dose.

9.2.8 Concomitant medications

Concomitant medications will be coded to generic terms using the World Health Organization Drug Dictionary (WHODD). The listing will include dosing date,

WHOdd drug class, WHOdd preferred drug name, reported drug name, start and stop date, and whether the drug was taken after vaccination and up through Day 28 (± 2). The summary table will consist of numbers and percentages of subjects reporting each WHOdd drug class and preferred name within drug class.

9.2.9 Immunogenicity analysis

Immunogenicity parameters will be listed for all subjects and summarized and analyzed for the primary and secondary immunogenicity populations separately.

M2e and HAI specific IgG antibody titration curves will be established at each time point that data are available. At the start of the study volunteers will be scored as positive (IgG titers above an established negative baseline) or negative (IgG titers below the negative baseline) for pre-existing M2e or HAI specific IgG titers. The proportion of sero-negative volunteers who develop significantly positive antibody titers after immunization in each Group will be determined. The proportion of sero-positive volunteers who develop a significant rise in antibody titers after immunization in each Group will also be estimated. Standard statistical analyses will be used to distinguish significant changes in antibody titers. One-sided 95% lower confidence bound on the estimated proportion will also be constructed. All analyses will be based upon a per-protocol cohort with additional analysis performed for the intent-to-treat (ITT) cohort. The per protocol cohort is defined as all volunteers who complete both immunizations (VAX102 or placebo plus TIV).

Anti-M2e or HAI serum antibody titers will be listed and summarized for each time point that data are available. The mean change from baseline to Day 28 (± 2) in the log-transformed anti-M2e or HAI serum antibody reciprocal titers will be compared to zero within dose groups using t-tests. Analysis of variance (ANOVA) will be used to test for differences among dose groups, with Dunnett's test used to compare each dose group. Dose-response will be tested using vaccine and the amount of antigen in μg per group, coded as 1 μg or placebo. Pairwise comparisons will be used to evaluate differences between Groups. Proportion of subjects with an immune response at Days 14 (± 2) and 28 (± 2) will be compared among Groups using a Fisher's exact test or chi square test of association.

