DATA ANALYSIS	
Prior to analysis of primary outcome measures of safety and immunogenicity, integrity of study conduct and route of administration group comparability will be examined. M2e or HAI specific IgG antibody titration curves will be established at each time point. At the start of the study, volunteers will be scored as positive (IgG titers above an established negative baseline) or negative (IgG titers below the negative baseline) for pre-existing M2e or HAI specific IgG titers. The HAI GMT and the proportion of sero-negative volunteers who develop a four-fold or greater increase antibody titers after immunization in each group (A and B) will be determined. The HAI GMT and proportion of sero-positive volunteers who develop a significant rise in antibody titers after immunization in each group will also be estimated. Standard statistical analyses will be used to distinguish significant changes in antibody titers. One-sided 95% lower confidence bound on the estimated proportion will also be constructed. All analyses will be based upon a per-protocol cohort with additional analysis performed for the intent-to-treat (ITT) cohort.

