7.2.2 Specific Antibody Assays

A venous blood sample (approximately 10 mL) will be taken from each subject pre-vaccination on Day 0 and on Days 14 and 28 for the analysis of anti-M2e serum antibody titers and HAI antibodies.

The immunogenicity of the VAX102 vaccine will be evaluated by measuring the number of subjects who demonstrate seroconversion either by developing a measurable titer following vaccination or by showing a significant increase in anti-M2e serum antibody titers post-vaccination. Standard statistical tests will be used to define a significant rise in antibody titers.

In addition to HAI titers (H1, H3 and B components), sera Days 0, 14 (± 2) and 28 (± 2) will also be evaluated for microneutralization titers, anti-flagellin titers using a panel of exploratory assays.

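### The between-group HAI comparison in Section 9.2.9 names no baseline covariate although every Day 0 titer is collected; ANCOVA on log Day 0 titer would probably be more precise and needs no new data

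*Protocol*

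**What the plan says.** Section 9.2.9 names the quantity analysed as "The mean change from baseline to Day 28 (± 2) in the log-transformed anti-M2e or HAI serum antibody reciprocal titers". This "will be compared to zero within dose groups using t-tests. Analysis of variance (ANOVA) will be used to test for differences among dose groups". In full, the between-group sentence reads: "Analysis of variance (ANOVA) will be used to test for differences among dose groups, with Dunnett's test used to compare each dose group". A dose-response test with the dose coded as 1 µg or placebo comes next, and then: "Pairwise comparisons will be used to evaluate differences between Groups". The response variable of the ANOVA is not restated. Change from baseline is the natural reading, because the preceding sentence defines it, but it is an inference.

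The baseline is available. Section 7.2.2 states: "A venous blood sample (approximately 10 mL) will be taken from each subject pre-vaccination on Day 0 and on Days 14 and 28". Baseline status is used elsewhere, but only to divide subjects when response is described. An example is in the synopsis under Data Analysis: "The HAI GMT and proportion of sero-positive volunteers who develop a significant rise in antibody titers after immunization". The mean-titer comparison makes no use of it beyond the subtraction.

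The second of the two secondary objectives (Section 2) is the TIV response with VAX102 against TIV alone. The rationale in Section 1 asks whether VAX102 acts as an adjuvant for TIV.

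**The concern.** The adjuvant question is a contrast between the two groups on HAI titer, with 40 subjects in each (Table 6). A change score fixes the slope of the Day 28 log titer on the Day 0 log titer at 1. If the true slope differs from 1, the change score has a larger variance than an analysis that estimates the slope. A chance difference in baseline titer between the groups then also passes into the estimated effect. In influenza serology subjects with higher starting titers may show smaller fold-rises, which is a slope below 1. The protocol's own division into sero-negative and sero-positive subjects treats the starting level as relevant.

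The within-group t-test against zero does not help with HAI, because both groups receive a standard dose of TIV and a rise is expected in both.

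At stake is precision on a secondary objective, in a trial whose sample size Section 9.2.2 calls arbitrary.

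**Working it through.** **Inputs from the protocol.** Two groups, 1:1, 40 each (Sections 3 and 4.1). Day 0 and Day 28 titers in every subject (Section 7.2.2). Two-sided 95% intervals for group differences (Section 9.2.5). Section 9.2.2 gives no SD, correlation, effect size or power, so there is no figure of the plan to reproduce.

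**Assumed inputs.** ρ is the correlation of Day 0 and Day 28 log titers. r = SD(Day 0)/SD(Day 28). σ is the Day 28 SD.

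**Variance per subject.**
- Change score: σ²(1 + r² − 2ρr)
- ANCOVA: σ²(1 − ρ²)
- Proportional gain of ANCOVA: (r − ρ)² / (1 + r² − 2ρr)

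The gain is a square over a variance, so in large samples it is never negative. It is zero only when r = ρ, that is, when the slope ρ/r equals 1. With r = 1 it simplifies to (1 − ρ)/2.

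Example, r = 0.75 and ρ = 0.5: 0.25² / (1 + 0.5625 − 0.75) = 0.0625/0.8125 = 7.7%.

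| r | ρ = 0.3 | ρ = 0.5 | ρ = 0.7 |
|---|---|---|---|
| 1.25 | 49.8% | 42.9% | 37.2% |
| 1 | 35.0% | 25.0% | 15.0% |
| 0.75 | 18.2% | 7.7% | 0.5% |
| 0.5 | 4.2% | 0.0% | 7.3% |
| 0.25 | 0.3% | 7.7% | 28.4% |

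At r = 1, widening ρ to 0.1 and 0.9 gives 45% and 5%.

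**Cost of estimating the slope.** At N = 80 the ANCOVA variance is inflated by about 1 + 1/(80 − 4) = 1.013. A simulation with 40 per group and 10,000 runs per scenario agrees. At r = 1 the gains are 34%, 24% and 13% for ρ of 0.3, 0.5 and 0.7. At r = ρ = 0.5, where the formula gives zero, there is a loss of 1.5%. At r = 0.25 and ρ = 0.3 the loss is 1.2%.

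**What the equal-SD case is worth.** The variance ratio is (1 + ρ)/2 = 0.65, 0.75 and 0.85. Forty per group with ANCOVA then equals 40/0.65 = 61.5, 40/0.75 = 53.3 and 40/0.85 = 47.1 per group with change scores. A difference that change scores would detect with 80% power is detected with about 94%, 90% and 86%.

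**Baseline imbalance.** Let d be the chance difference between groups in mean log Day 0 titer. Given d, the change-score estimate is shifted by (ρ/r − 1)·d. With r = 1 and ρ = 0.5 the shift is −0.5d, so the group that starts higher appears to respond less. With r = ρ the shift is zero. Over repeated randomizations d averages zero.

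**M2e.** Section 1 says that M2e antibody is very low or undetectable in human sera. A nearly constant baseline puts r near 0, where the gain is about ρ². An assay floor is likely to keep ρ small as well, so little gain is expected.

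**Number of distinct tests.** With two groups, a one-way ANOVA is the two-sample t-test, Dunnett's test has one comparison, a dose trend coded 1 µg or placebo has two points, and there is one pair. All four sentences reduce to the same A-versus-B contrast.

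**The case against.** The strongest reply is that this is a preference about efficiency. Under 1:1 randomization a comparison of change scores is valid. Safety is the primary objective, the synopsis lists the HAI comparison as descriptive, and no decision threshold rests on it. Covariates are often left to the SAP, which is not at hand, and Section 9.2.9 does not exclude one. All of this stands, and it limits the weight of the point. What remains is that the protocol states a specific method, and a better use of data already collected is available.

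A reader might go further in four ways that the documents do not support.

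- **That the analysis is biased and adjustment removes the bias.** Randomization leaves no bias on average. Only the estimate conditional on a chance imbalance is affected.
- **That the within-group t-tests say nothing about VAX102.** This is wrong for M2e. Section 1 says current vaccines do not induce an appreciable M2e response, so a rise in Group A does bear on the first secondary objective. For HAI the t-tests do not stand in for a group comparison, because one is also planned.
- **That a gain of 15% to 35% is a property of this trial.** It needs equal SDs and a correlation of 0.3 to 0.7, and neither is in the protocol.
- **That leaving out site is a defect.** The protocol describes no randomization stratified by site, and nothing in it shows what site adjustment would gain.

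**Conclusion.** The point holds as a recommendation on efficiency, confined mainly to the between-group HAI comparison. The planned analysis is valid but, on its natural reading, can give away precision that the Day 0 sample would supply.

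The size depends on two quantities that the protocol does not give. With equal SDs and a correlation of 0.3 to 0.7 the variance falls by 35% to 15%. With a Day 0 SD of 0.75 times the Day 28 SD it falls by about 18% to 0.5%, and with 0.5 times by 0 to 7%. A Day 0 SD above the Day 28 SD would give more. The downside is a loss of about 1 to 1.5%. The possible gain is therefore much larger than the possible loss, though a gain of any given size cannot be promised.

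**What to change.** In Section 9.2.9, replace the ANOVA, Dunnett, dose-response and pairwise sentences with wording such as:

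> For each HAI antigen (H1, H3, B), log titer at Day 28, and likewise at Day 14, will be compared between Groups A and B by ANCOVA with group and log Day 0 titer as terms. The adjusted GMT ratio A/B will be reported with a two-sided 95% confidence interval. Within-group changes in HAI titer will be summarized descriptively.

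The within-group M2e test may stay. The same ANCOVA can be applied to M2e for consistency, with little gain expected. Site may be added as a term but need not be.

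The cost is a change of wording and one degree of freedom per model, or two if site is included. No further subjects, visits or samples are needed. If the SAP already specifies this model, the protocol text only has to be brought into line with it.

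The choice should be fixed before treatment assignments are released.
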